Although TBS exhibits a promising future regarding clinical interventions, further randomized, placebo-controlled studies with an adequate sample size are needed to demonstrate the true efficacy of these techniques in the scope of neurorehabilitation.

The evaluation of neuroplasticity through the co-registration of TMS-EEG

The ability of the brain to modify its functions by strengthening or inhibiting synaptic connections, to readjust its structure and/or to create new neural connections in response to environmental changes, is defined as "neuroplasticity". Neuroplasticity is the basis of learning and memory processes which occur in healthy individuals throughout the lifespan, and is of crucial importance in the scope of recovery phenomena that occur in patients following brain damage. Currently, knowledge regarding cerebral modifications related to recovery induced by treatment of neurological deficits is still limited.

Similarly, the neural mechanisms responsible for clinical improvements induced by the application of brain stimulation techniques are, for the most part, unknown. The general idea behind the use of brain stimulation is that it is able to induce changes in cortical excitability which leads to recovery and/or a reorganization of the functional networks responsible for the decline of cognitive function (Miniusi and Rossini, 2011). TMS-EEG co-registration, an innovative integrated multimodal imaging technique combines the application of single TMS pulses with electroencephalogram (EEG) recording, and its characteristics are particularly relevant to this project (Bortolotto et al., 2015). In fact, thanks to EEG recording of responses induced by TMS it is possible to test both local excitability as well as the connectivity of the cortical networks on a large scale, since activation induced by TMS in the stimulated area propagates to distant but functionally connected cortical regions.

OBJECTIVES

Primary objective:

- To evaluate the clinical, cognitive and functional efficacy of brain stimulation as a treatment, applied to patients diagnosed with mild cognitive decline (MCI) and Alzheimer's dementia (AD) in order to verify whether TBS in conjunction with cognitive rehabilitation produces better results than results obtainable through the use of only one of the two methods evaluated, based on the score of the Mini Mental State Examination or MMSE and on the scores of individual neuropsychological tests.

Secondary objectives:

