All patients included in the study will be randomly assigned to one of five different treatment protocols (20 patients diagnosed with AD and 20 patients diagnosed with MCI for each protocol), balanced using MMSE and age results so that the groups are homogeneous. In detail, the protocols are:

1. Combination of continuous TBS and cognitive training (cTBS + CT);
2. Combination of TBS in intermittent mode and cognitive training (iTBS + CT);
3. Isolated application of TBS in continuous mode (cTBS);
4. Isolated application of TBS in intermittent mode (iTBS);
5. Isolated application of cognitive training (with placebo TBS) (CT).

The treatment involves two main phases (Figure 1): 1) an intensive phase, lasting 2 weeks, with a daily frequency (5 times a week, for a total of 10 sessions); 2) a subsequent maintenance phase, lasting 5 weeks, with a biweekly frequency (2 times a week, for a total of 10 sessions).

Patients will undergo a clinical and neuropsychological evaluation and a neurophysiological evaluation before the start of treatment (baseline, t0), at the end of the intensive phase of treatment (t1), at the end of the maintenance phase (t2), and after 3 (t3) and 5 months (t4) from the start of treatment (Figure 2).

Figure 2. Study Design

Months Weeks	1				2				3				4				5				6				
	1	2	3	4	5	6	7	8	9	10	11	12	13	14	15	16	17	18	19	20	21	22	23	24	
Rehabilitative Treatment																									
Combined TBS +Cognitive Training (n. sessions)	5	5	2		2	2	2	2																	
Cognitive Training only (n. sessions)	5	5	2		2	2	2	2																	
TBS application only (n. sessions)	5	5	2		2	2	2	2																	
Evaluations																									
Clinical and Neuropsychological Evaluation	T0				T1				T2				T3								T4				
Neurophysiological Evaluation	T0				T1				T2				T3								T4				

 Intensive Treatment Phase
 Maintenance Phase

PATIENTS

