The rehabilitation of memory functions, associated with the stimulation of the left DLPFC, will be focused on learning face-name associations. The face-name association training involves an acquisition phase in which patients are shown faces with an associated name and are asked to memorize these associations. The reproduction phase follows the training phase, in which the patient's task will consist of finding the face that corresponds to the associated name. Based on the patient's performance, the level of difficulty will be modulated by increasing or decreasing the number of associations to be memorized and possibly, for higher difficulty levels, by adding other information to be memorized (for example, a profession).

Neuropsychological and psychological evaluation

All patients will undergo a neuropsychological assessment before the start of treatment (t0), at the end of the intensive treatment phase (t1), at the end of the maintenance phase (t2), and after 3 (t3) and 5 months (t4) from the start of treatment (Figure 1).

The evaluation of the patients after some time (follow-up) from the end of the treatment will allow for the verification of long-term effects.

A possible “practice effect” resulting from the repeated and quick administration of neuropsychological tests is expected and will be considered in the data analysis, as in all experimental protocols of this type. The practice effect is a factor common to all experimental groups and does not affect the evaluation of the efficacy of the treatment, the primary objective of the study.

Neuropsychological assessment involves the administration of a series of standardized tests designed to investigate specific cognitive domains, such as: global cognitive functioning (*Mini Mental State Examination, MMSE*); abstract non-verbal reasoning (*Raven's Colored Progressive Matrices*); short and long term memory, both verbal and visuospatial (*Digit Span; Spatial Span; Prose Memory; Free And Cued Selective Reminding Test*; deferred re-enactment of the *Complex Figure by Rey Osterrieth*); linguistic production (*token test, semantic fluency; phonemic fluency*); attention and executive functions (*Multiple Features Cancellation task; Trial Making test; Stroop test; attentional matrices*); and practical and visual-constructive skills (*Copy of Rey's Complex Figure*).

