- 2) Connectivity evoked by TMS (TMS evoked connectivity): the latencies and topographical distribution of the TEPs, both at the sensor level on the scalp, and through source analysis, will represent a connectivity index and will be used to infer how the induced activity propagates from the stimulation site to functionally connected areas.
- 3) TMS evoked oscillations (TMS evoked oscillations): An analysis of the responses induced by TMS in the frequency domain will allow us to obtain information on the intrinsic capacity of the stimulated area to generate oscillatory activity in specific frequency bands [wavelet, synchronization and event-related desynchronization (ERS / ERD) and coherence].

The characterization and organization of brain networks will be investigated using graph theory (Stam et al. 2007).

STATISTICAL ANALYSIS

The variables that will be considered for the analysis of clinical, neuropsychological and neurophysiological data are: a) treatment effect over time (t0, t1, t2, t3, t4); b) type of treatment protocol (combination of TBS and cognitive training, isolated application of TBS, isolated application of cognitive training); c) type of stimulation protocol (cTBS, iTBS) and d) clinical group (AD or MCI). The experimental design will be both "within subjects" within each variable of interest (for example, investigating the difference between t1 and baseline to evaluate the effect of intensive treatment), and "between subjects" regarding the data between the different treatment protocols (for example, investigating the difference between combination of TBS and cognitive training and isolated application of TBS, to evaluate which protocol produces the greatest benefits), between different stimulation protocols (for example, investigating the difference between cTBS and iTBS to evaluate which protocol produces greater benefits) and between clinical conditions (to assess whether the same treatment leads to differences in the achieved benefit between the two groups of patients, AD and MCI).

Calculation of sample size

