The primary outcome for the calculation of the sample size was defined as the effect of the cTBS protocol and the iTBS protocol (both in combination with cognitive training) compared to the treatment involving the combination of cognitive training with TBS placebo and the one which involves only the TBS protocol applied in isolation, on the MMSE score obtained at the end of the treatment. Based on the results of a previous rTMS study on a sample of AD patients (Ahmed et al., 2012), we estimate that at the end of our treatment there will be an improvement in the MMSE score of at least 3 points (SD of change = 2.95) for protocols that involve the combination of cognitive training and real TBS, and of 0.2 points (SD of change = 2.7) for the treatment that involves the combination of cognitive training and placebo TBS.

Considering an alpha value of 0.05 and a power of 0.80, we estimate that the number of patients to be recruited should be 16 patients per group, increased to 20 per group to take into account a possible dropout rate of 20%.

Techniques provided for data processing

Behavioral and neurophysiological data will be analyzed by analysis of variance (ANOVA) and post-hoc comparisons (t-test, contrast analysis).

Statistical processing software

Data processing will be performed with BrainVision Analyzer, SPSS and/or Statistica software.

ETHICAL CONSIDERATIONS AND ASSESSMENT OF THE RISK/BENEFIT RATIO

Expected benefits

Based on the assumptions of the present project, patients who will receive the treatment that involves the combined application of rTMS and cognitive training should show a clinical response, based on the primary endpoints reported above, better than the patients assigned to the protocols in which rTMS and cognitive training are applied in isolation. The research also provides indirect scientific/cognitive benefits, in terms of advancing knowledge on the development of treatments with proven efficacy and on the mechanisms underlying Alzheimer's dementia.

Potential Risks

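### Within-subject change in MMSE and the neuropsychological tests is read as a treatment effect, although the protocol expects a practice effect that this contrast cannot remove (minor)

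*Protocol*

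**What the plan says.** The Statistical Analysis section of the protocol lists the analysis variables for clinical, neuropsychological and neurophysiological data together. The first is "a) treatment effect over time (t0, t1, t2, t3, t4"). As its example of the within-subject part, the section gives "investigating the difference between t1 and baseline to evaluate the effect of intensive treatment". The example of the between-subject part compares treatment protocols, "to evaluate which protocol produces the greatest benefits".

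The section on neuropsychological and psychological evaluation places MMSE, the primary measure, in the test battery that is repeated at t0 to t4. It says that a practice effect from this repetition "is expected and will be considered in the data analysis, as in all experimental protocols of this type". It then calls practice a factor "common to all experimental groups and does not affect the evaluation of the efficacy of the treatment, the primary objective of the study".

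The primary objective is comparative: whether TBS with cognitive rehabilitation "produces better results than results obtainable through the use of only one of the two methods evaluated". Study Design has five arms: two combine real TBS with training, two give real TBS alone, and the fifth is described as "Isolated application of cognitive training (with placebo TBS) (CT").

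**The concern.** A practice gain shared by all arms cancels when change is compared between arms. It does not cancel when a patient's t1 score is compared with that patient's own baseline, or when change is averaged over arms to give the time main effect. Both of those quantities contain treatment, practice and any other time trend. The protocol's only stated reason for setting practice aside is that it is common to all groups, and that reason does not reach the within-subject contrast which the statistical section reads as an effect of treatment.

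The design offers no way round this. No arm is untreated or sham for both components, so no arm shows retest gain alone. If the example is followed for cognitive scores, a rise at t1 could be reported as an effect of the intensive phase when some or all of it is retest gain. The temptation is greatest for TBS alone, which has no sham-only comparator.

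**Working it through.** **The plan's own figure.** The Calculation of sample size section assumes a 3-point gain (SD of change 2.95) in the combined arms and a gain "of 0.2 points (SD of change = 2.7) for the treatment that involves the combination of cognitive training and placebo TBS", with alpha 0.05 and power 0.80.

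- Difference: 3 − 0.2 = 2.8. Average SD: √[(2.95² + 2.7²)/2] = 2.83.
- Normal approximation, two-sided: n = 2(1.960 + 0.842)² × (2.83/2.8)² = 16.01 per group, against the stated 16. Power at 16 is 79.97% by this formula and 77.3% by noncentral t.
- Dropout: 16/(1 − 0.20) = 20, as stated.

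The sample size concerns a between-arm difference and is not in dispute.

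**What practice does to each contrast.** Write the mean change from t0 to t1 in arm j as Dⱼ = τⱼ + π, where τⱼ is the treatment effect and π the common practice gain.

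- Within one arm: Dⱼ = τⱼ + π. Practice remains in full.
- Time main effect, averaged over arms: mean(τⱼ) + π. Practice remains in full.
- Between arms: Dⱼ − Dₖ = τⱼ − τₖ. Practice cancels.

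To estimate π from the trial, one arm would need τ = 0 by design. None of the five has it.

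**Size, under assumed gains.** The protocol gives no value for π; 0.2, 0.5 and 1.0 MMSE points are assumptions. Other inputs: no treatment effect; SD of change 2.7 (sample size section, based on an AD sample and stated for end of treatment, carried here to t1); two-sided 5% paired test. The noncentrality is (π/2.7)√n with n − 1 degrees of freedom, and the critical value is 2.131 for n = 16 and 2.093 for n = 20.

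| Assumed gain | n = 16: noncentrality | n = 16: rejection | n = 20: noncentrality | n = 20: rejection |
|---|---|---|---|---|
| 0 | 0 | 5.0% | 0 | 5.0% |
| 0.2 | 0.296 | 5.9% | 0.331 | 6.1% |
| 0.5 | 0.741 | 10.7% | 0.828 | 12.3% |
| 1.0 | 1.481 | 28.4% | 1.656 | 35.0% |

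- Rejection reaches 10% at a gain of 0.47 points (n = 16) or 0.41 points (n = 20).
- With the SD of 2.95 the rates for n = 16 are 5.7%, 9.7% and 24.6%, and for n = 20 they are 6.0%, 11.1% and 30.2%.
- Simulation with SD 2.7 (200,000 runs) gives 5.9%, 10.7% and 28.5% for n = 16, and 6.1%, 12.3% and 34.8% for n = 20.
- The time main effect is more exposed because it pools arms. As an approximation, a one-sample test on 5 × 16 = 80 AD completers with SD 2.7 rejects in 10%, 37% and 91% at 0.2, 0.5 and 1.0 points.
- Between arms, 16 against 16 with the same gain in both, simulated rejection is 5.1%, 5.0% and 4.9%.

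No separate figure is given for MCI, because the protocol states no SD of change for MCI.

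**The case against.** The strongest reply is that this is a remark on wording. The contrast is a parenthetical example of what within-subject means, and no success criterion rests on it. The factor label could be read as the course of the treatment effect over t0 to t4. The protocol anticipates practice, promises to consider it, and rightly says that the comparative evaluation is protected; how it will be handled may be in the SAP. The planned ANOVA with contrasts can supply arm-by-time comparisons. Retest norms or parallel test forms could also bring in information on practice from outside the trial.

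Much of this stands, and it is why the point is minor. It does not rescue the reading of t1 minus baseline, which is a stated inference and not a detail left open. A promise to consider practice cannot separate it within an arm from these five arms alone.

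A second reply concerns size. The planned total change with training and placebo TBS is only 0.2 points, and at that level the inflation in a single arm is negligible. This also stands for a single AD arm. However, 0.2 is a net change that could hide a practice gain offset by decline, and it says nothing of MCI or of the other tests.

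A third reply is that TMS-EEG has no untreated arm either. That is true, but the protocol ties practice to the neuropsychological tests, so the argument here does not extend to TMS-EEG.

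**Conclusion.** The concern holds as a minor error of interpretation, confined to MMSE and the neuropsychological tests. As written, the statistical section attributes within-subject change and the time factor to treatment, while the protocol itself expects practice to contribute to both. The size is unknown. With SD 2.7 and no true effect, the single-arm test is barely disturbed at an assumed 0.2 points and noticeably inflated from about half a point. These rates illustrate the mechanism and do not estimate what will happen in the trial. The randomised between-arm comparison, its type I error and the sample size are unaffected, provided practice is the same in all arms, as the protocol assumes.

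**What to change.** In the Statistical Analysis section, rename the first factor "time" and reword the within-subject example so that t1 minus baseline describes change over the intensive phase. State that, for MMSE and the neuropsychological tests, change from baseline and the time main effect are descriptive, and that efficacy statements rest on arm-by-time contrasts, that is, on between-arm differences in change. Within-subject TMS-EEG analyses can stay as they are on this point.

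The cost is the rewording of two phrases and the added statement. No new data are needed, and neither the sample size nor the primary comparison changes. The downside is that no efficacy claim for cognitive scores can be made for a single arm from its own change over time.

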The study will involve patients diagnosed with mild cognitive impairment (MCI) and patients diagnosed with mild to moderate Alzheimer's dementia (AD), male or female, right-handed, aged between 50 and 85 years (extreme inclusive) when the informed consent is signed, with normal or corrected vision through lenses. All patients must meet the inclusion criteria for TMS (see attached protocol). Patients will be selected on the basis of a clinical evaluation (neuropsychological test battery at the Neurocognitive Rehabilitation Center-CeRiN and, in accordance with the APSS, CSF and PET examination performed through nuclear medicine) and a further neuropsychological evaluation related to the research (see paragraph Neuropsychological evaluation).

Inclusion criteria for patients diagnosed with Alzheimer's dementia:

- Diagnosis of Alzheimer's dementia
- Mini Mental State Examination (MMSE) score ≥ 16 ;
- Stable intake of cholinesterase inhibitors for at least 3 months before the start of the protocol;
- Be able to provide information regarding their cognitive and functional skills, or have a caregiver available who is able to provide the patient information necessary for participation in the study and who is present when signing the patient's informed consent.

Inclusion criteria for patients diagnosed with mild cognitive impairment:

- Diagnosis of mild cognitive impairment
- Mini Mental State Examination (MMSE) score ≥ 24 ;
- Be able to provide information regarding their cognitive and functional skills, or have a caregiver available who is able to provide the patient information necessary for participation in the study and who is present when signing the patient's informed consent

Common exclusion criteria:

- Patients who are unable to perform the tasks required by the experimental procedure;
- History and / or evidence of any other central nervous system disorder that could be interpreted as a cause of dementia such as, for example, structural or developmental abnormality, epilepsy, infectious diseases, degenerative or inflammatory/demyelinating diseases of the central nervous system such as Parkinson's disease and Frontotemporal dementia;
- History of significant psychiatric disease which, in the investigator's judgment, could interfere with study participation;
- History of alcohol or other substance abuse, according to DSM-V criteria, or recent or previous history of drug abuse if this could be a contributing factor to dementia;

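### Allocation is balanced on MMSE and age, but the planned ANOVA and t-tests adjust for neither baseline score nor age, so precision is given up at no saving

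*Protocol*

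**What the plan says.** Under Study Design, each of five arms receives 20 AD and 20 MCI patients, and allocation is "balanced using MMSE and age results so that the groups are homogeneous".

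The Statistical Analysis section gives its own list of variables. It opens "The variables that will be considered for the analysis of clinical, neuropsychological and neurophysiological data are: a) treatment effect over time" (t0 to t4) and continues "b) type of treatment protocol (combination of TBS and cognitive training, isolated application of TBS, isolated application of cognitive training", then stimulation protocol (cTBS or iTBS) and clinical group (AD or MCI). One stated between-subject aim is "to assess whether the same treatment leads to differences in the achieved benefit between the two groups of patients, AD and MCI". The method, under Techniques provided for data processing, is: "Behavioral and neurophysiological data will be analyzed by analysis of variance (ANOVA) and post-hoc comparisons (t-test, contrast analysis").

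The sample size is planned on changes in MMSE. The combination arms are expected to show "an improvement in the MMSE score of at least 3 points (SD of change = 2.95"), and CT with placebo TBS a gain of 0.2 points (SD of change 2.7). From this, "we estimate that the number of patients to be recruited should be 16 patients per group, increased to 20 per group" for 20% dropout.

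Under Patients, the AD criterion is "Mini Mental State Examination (MMSE) score ≥ 16" with no upper limit, the MCI criterion is 24 or more, and ages run from 50 to 85.

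**The concern.** The protocol treats MMSE and age as important enough to balance on, then leaves both out of the model. Baseline is used, but only as the t0 level of the time factor. An arm contrast against t0 therefore subtracts the whole baseline value instead of estimating its slope, and the part of the change that baseline predicts stays in the error term. The clinical-group factor does not absorb it, because the entry criteria leave a wide spread of MMSE and age within each diagnosis.

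No bias or inflated type I error is at stake. Two things are lost:

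- **Precision.** This matters most where patients are fewest: one combination arm against CT within one diagnosis, and the question whether AD and MCI benefit differently.
- **Part of the benefit of balancing.** If arms are forced to be alike on baseline and the analysis ignores this, the standard error is overstated and the test is conservative.

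**Working it through.** **Inputs.** From Calculation of sample size: difference 3 − 0.2 = 2.8 points; SDs of change 2.95 and 2.7; alpha 0.05 (sidedness not stated, two-sided taken); power 0.80; 16 evaluable per arm. From Study Design: the arms are equal in size within each diagnosis. The correlation r between baseline and end-of-treatment MMSE is not in the protocol; 0.5 to 0.8 is assumed, with 0.9 as a less favourable case.

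**The protocol's own figure.** Pooled variance = (2.95² + 2.7²)/2 = 7.996, SD 2.828. Normal approximation: n = 2 × 7.996 × (1.960 + 0.842)² / 2.8² = 16.01. This reproduces 16 per group, and 16/0.80 = 20. The sizing is thus a change-score comparison of one arm with another. With the exact t distribution (30 df) power at 16 per group is 0.773. With pooled ANOVA error it is 0.790 (five arms in one diagnosis, 75 df) to 0.795 (both diagnoses, 150 df).

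**Effect of adjustment.** Let the score have SD s at both times. The change score has variance 2s²(1 − r); the baseline-adjusted analysis has residual variance s²(1 − r²). The ratio is (1 + r)/2: 0.75 at r = 0.5, 0.90 at 0.8 and 0.95 at 0.9. Confidence intervals shrink by the square root of this, about 13%, 5% and 3%. Holding the SD of change at 2.83, the implied MMSE SD is 2.83/√(2(1 − r)): 2.8 at r = 0.5 and 4.5 at r = 0.8.

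Unadjusted SE = √(2.95²/n₁ + 2.7²/n₀). The adjusted SE multiplies this by √((1 + r)/2), with one degree of freedom less. Power is from the noncentral t.

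| Comparison | SE | Unadjusted | Adjusted, r = 0.5 | Adjusted, r = 0.8 |
|---|---|---|---|---|
| One combination arm vs CT, one diagnosis (16 vs 16), power | 1.000 | 0.773 | 0.878 | 0.814 |
| Same, pooled error within the diagnosis (75, then 74 df), power | 1.000 | 0.790 | 0.891 | 0.830 |
| Both combination arms vs CT, one diagnosis (32 vs 16), power | 0.853 | 0.895 | 0.960 | 0.923 |
| Same, 95% half-width in points | 0.853 | 1.72 | 1.49 | 1.63 |
| AD-vs-MCI difference in that benefit, 95% half-width | 1.206 | 2.40 | 2.07 | 2.27 |
| One combination arm vs CT, diagnoses pooled (32 vs 32), power | 0.707 | 0.974 | 0.994 | 0.984 |
| Both combination arms vs CT, diagnoses pooled (64 vs 32), power | 0.603 | 0.996 | 0.9996 | 0.998 |

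The SE for the AD-vs-MCI row is √2 × 0.853 = 1.206. At r = 0.9 the first row gives 0.793 and the second 0.810.

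**Effect of balancing.** The protocol does not say how tightly arms are balanced, so two schemes were simulated for MMSE, 16 vs 16, common SD of change 2.83 (60,000 null and 40,000 alternative runs):

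| Scheme | r | Type I error, unadjusted / adjusted | Power, unadjusted / adjusted |
|---|---|---|---|
| No balancing | 0.5 | 0.048 / 0.051 | 0.777 / 0.868 |
| No balancing | 0.8 | 0.049 / 0.050 | 0.772 / 0.798 |
| Median split | 0.5 | 0.033 / 0.049 | 0.790 / 0.874 |
| Median split | 0.8 | 0.044 / 0.051 | 0.779 / 0.808 |
| Pairwise matching (upper bound on tightness) | 0.5 | 0.024 / 0.050 | 0.799 / 0.877 |
| Pairwise matching (upper bound on tightness) | 0.8 | 0.040 / 0.051 | 0.786 / 0.816 |

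With balancing, the unadjusted test falls below its nominal 5%; the adjusted test holds it. Without balancing, adjusted power is slightly below the formula because of chance imbalance.

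**The case against.** The strongest reply is that covariates are ordinary SAP material, that the protocol nowhere excludes them, and that baseline is already used through t0. The last point is right and limits the finding: only the step from change score to baseline adjustment is lost. On the first, the protocol is not silent. It gives its own variable list and names its method, and neither contains the factors it balances on. A SAP could add them, but that would extend what the protocol states.

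Several points on size stand:

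- The gain rests on an assumed r. At r = 0.9 it is about two points of power.
- Because the plan is ANOVA with contrasts, pooled error is a fair reference. Like for like, 0.790 becomes 0.891, 0.830 or 0.810 at r = 0.5, 0.8 or 0.9, a gain of about 10, 4 or 2 points.
- Only the narrowest comparison sits near 0.80. Taking both combination arms together, or pooling diagnoses, is already well powered.
- The SDs come from an AD sample. The AD-vs-MCI and pooled rows carry them to MCI, where entry at 24 or more restricts the range and an SD of 4.5 is doubtful. With the SD of change held, a smaller MMSE SD implies a lower r, which favours adjustment, but those rows are illustrative for MCI.
- The gain from age cannot be computed from the protocol.

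It is also said that t0 cannot be both a covariate and a level of time. That affects how the model is written, not whether to adjust. It arises only for between-arm comparisons, and the within-patient comparison of t1 with baseline can stay as planned.

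**Conclusion.** The point holds, as a free improvement rather than the correction of an error. The stated sample size is not wrong because of it, and the unadjusted analysis is valid, conservative to the extent that balancing is tight. Adjusting for baseline would make every between-arm confidence interval for MMSE about 13% to 5% narrower. It would lift the comparison on which the trial was sized from just below its 0.80 target to 0.81 to 0.88. At r = 0.9 the gain is small.

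These figures assume equal SDs at t0 and end, a linear baseline effect, and r between 0.5 and 0.8. The direction is secure across that range; the size is uncertain. The change should be made, with medium confidence in how much it buys.

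**What to change.** In the Statistical Analysis section, state that between-arm comparisons of MMSE, the neuropsychological scores and the TMS-EEG indices will be adjusted for the t0 value of the same outcome, baseline MMSE and age, by ANCOVA or an equivalent repeated-measures model. For MMSE, the t0 value is the baseline MMSE and enters once. Fit arm as a five-level factor and obtain the stated comparisons as contrasts: combination vs CT, combination vs TBS alone, cTBS vs iTBS, and the AD-vs-MCI difference in benefit. Where t0 is a covariate, the outcome levels of time are t1 to t4; the within-patient comparisons with t0 remain separate.

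The cost is a short addition to the text, two or three degrees of freedom, an assumed linear baseline effect and slightly more modelling. The named SPSS software fits such models, and no extra patients, visits or measurements are needed.

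### ANOVA with t-tests over five visits uses incomplete records poorly although 20% dropout is expected; a mixed model with the contrast at end of treatment would keep the data

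*Protocol*

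**What the plan says.** The Statistical Analysis section of the protocol lists the variables to be analysed, beginning with "a) treatment effect over time (t0, t1, t2, t3, t4", and describes the design as within subjects for such variables and between subjects for treatment protocol, stimulation type and diagnosis. Its example of a within-subject comparison is t1 against baseline.

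Under Techniques provided for data processing, one method is named: "Behavioral and neurophysiological data will be analyzed by analysis of variance (ANOVA) and post-hoc comparisons (t-test, contrast analysis". The listed software includes SPSS.

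Under Calculation of sample size, the primary outcome is MMSE at the end of treatment. The Study Design section puts the end of the maintenance phase at t2, with t3 and t4 as later follow-up, so the end of treatment is taken here as t2. The inputs are "an improvement in the MMSE score of at least 3 points (SD of change = 2.95") for the combined arms and "of 0.2 points (SD of change = 2.7) for the treatment that involves the combination of cognitive training and placebo TBS". The result is "16 patients per group, increased to 20 per group to take into account a possible dropout rate of 20"%. The Study Design section applies this within each diagnosis: "20 patients diagnosed with AD and 20 patients diagnosed with MCI for each protocol".

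The Informed consent section lets participants withdraw at any time. The protocol does not say that incomplete records are deleted, and it does not name a mixed model.

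**The concern.** A classical repeated-measures ANOVA with a five-level time factor needs a value at every level. A patient seen at t0, t1 and t2 but not at t4 drops out of the model altogether, although the value that the primary question needs was recorded. A patient who leaves between t1 and t2 is lost to the end-of-treatment comparison under any ANOVA or t-test reading, although the t1 score says something about where that patient was heading.

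Two things are at stake. One is precision, in groups of 20 within each diagnosis. The other is validity: a comparison of those who stayed can be shifted if leaving depends on how the patient is doing and this dependence differs between arms.

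The point is not that a missing-data rule or an analysis set is absent; those may stand in an analysis plan that is not shown. It is that the protocol itself selects a method that handles partial records poorly, next to its own forecast of one patient in five lost.

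**Working it through.** **Inputs from the protocol.** Improvement of 3 versus 0.2 points, so a difference of 2.8. SDs of change 2.95 and 2.7. Alpha 0.05 and power 0.80. Group size 16, raised to 20 for 20% dropout. Two-sided testing is assumed because sidedness is not stated.

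**The plan's own figure.**
- Pooled SD = √((2.95² + 2.7²)/2) = √7.996 = 2.828. Standardised difference d = 2.8/2.828 = 0.990.
- Normal approximation: n = 2 × (1.960 + 0.842)²/0.990² ≈ 16.0 per group. At n = 16 the power is 79.97%; strict rounding up gives 17.
- Dropout: 16/0.8 = 20.

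The sample size therefore reproduces. Losing exactly the planned 20% leaves the planned power.

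**Power by the t-test** (noncentral t, df = 2n − 2, noncentrality d√(n/2)):

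| n per group | power |
|---|---|
| 20 | 0.86 |
| 18 | 0.82 |
| 16 | 0.77 |
| 14 | 0.71 |
| 13 | 0.68 |

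The step from 0.80 to 0.77 at n = 16 comes from using the t distribution instead of the normal and has nothing to do with missing data.

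**Discarded t2 data under a five-visit ANOVA.** 20% of 20 is 4 patients. Assume one is lost before each of t1, t2, t3 and t4. Then 20 − 2 = 18 are seen at t2 and 20 − 4 = 16 have all five visits. The five-visit analysis uses 16 (0.77); keeping everyone seen at t2 uses 18 (0.82). The range depends on timing. If all four leave before t2, both analyses have 16 and the gap is nil. If all four leave after t2, it is 16 against 20, or 0.77 against 0.86.

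**Missed visits on top of dropout** (rates assumed). With a fraction m missed independently at each of four post-baseline visits, complete records per group = 20 × 0.8 × (1 − m)⁴:
- m = 2%: 14.8, power 0.74
- m = 5%: 13.0, power 0.68
- m = 10%: 10.5, power 0.58

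**Bias of a completers' comparison.** If a fraction p of an arm leaves and leavers do x points worse than stayers, the stayers' mean exceeds the arm's true mean by p·x. The difference between arms A and B is then shifted by p_A·x_A − p_B·x_B. Assume exits of 30% and 10% and the same x in both arms:
- x = 1: 0.3 − 0.1 = 0.2 points (7% of 2.8)
- x = 2: 0.6 − 0.2 = 0.4 points (14%)
- x = 3: 0.9 − 0.3 = 0.6 points (21%)

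Swapping the exit rates reverses the sign. With x = 0 in both arms the shift is zero whatever the exit rates. With equal exits and equal x it is also zero. With equal exits of 20% but x = 2 in one arm and 0 in the other, it is 0.2 × 2 = 0.4.

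**The case against.** The protocol says ANOVA; it does not say repeated-measures ANOVA on complete cases. Its within-subject example is a single visit against baseline, and the sample size rests on SDs of change. A t2-minus-t0 test would keep every patient seen at t2, whatever happened at t3 or t4. This stands: the exclusion follows from one natural reading, supported by five time levels and by t-tests described as post hoc, but it is not stated. On the other reading only the patients without t2 are lost, and the gain in power from a mixed model would be small.

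A reader might infer that the expected 20% dropout itself leaves the trial underpowered, or that enlarging 16 to 20 shows a completers' analysis is planned. Neither follows. The enlargement pays for that loss, and it is routine whatever the analysis.

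A reader might also infer that unequal exits alone bias the result, or that training burden makes large imbalances likely. Unequal exits do no harm unless leaving is related to outcome. Training burden separates the combined arms from TBS alone, but not from training with placebo TBS, where both arms have the same training and patients are blinded. The 30% versus 10% figures are illustrative. Even 0.6 points is below the standard error of the difference at 16 per group, 2.828 × √(2/16) = 1.0.

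Finally, the power figures are for one diagnosis. If both diagnoses are pooled, 32 per arm gives 0.97, and the loss matters much less.

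**Conclusion.** The concern holds as a weakness in the fixed method, not as an error of calculation or a contradiction. On either reading, patients who leave between t1 and t2 add nothing to the end-of-treatment comparison despite a measured t1. On the five-visit reading, those who miss only t3 or t4 also lose a valid t2 score.

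For one pairwise comparison within one diagnosis, the avoidable cost on the five-visit reading is about 0.05 in power (0.77 against 0.82) with evenly spread dropout. Depending on when patients leave it ranges from nothing to about 0.09, and it grows if visits are also missed. Bias is possible but cannot be sized from the protocol; 0.2 to 0.6 points is what the stated assumptions produce. The change is worth making because it is cheap and improves the analysis on both readings.

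**What to change.** Under Techniques provided for data processing, make the primary analysis of MMSE a linear mixed model for repeated measures, with visit as a categorical factor, treatment arm, diagnosis and their interactions, and an unstructured covariance. Include every randomised patient with any post-baseline visit, in the assigned arm, and estimate the primary contrast at t2. Keep the complete-case ANOVA as a sensitivity analysis, and report exits by arm and visit.

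The cost is one paragraph of text. No new data or visits are needed, and SPSS, already named in the protocol, can fit the model. The downside is small: the model assumes that data are missing at random given the observed visits, so it does not correct for exits driven by later decline that nobody measured.
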